### **15.3.1 Definitions**

#### **15.3.1.1 Adverse Event/Experience**

An Adverse Event/Experience is any unexpected or undesirable experience occurring to a subject during a study, which may or may not be related to a test material. All adverse event/experiences will be recorded and reported using Adverse Event documents according to the Standard Operating Procedures of the testing facility.

All Adverse Events, regardless of severity or the cause/effect relationship, are to be recorded. The severity of the effect will be noted as "Mild," "Moderate," or "Severe" according the following definitions:

Mild	Awareness of sign(s) or symptom(s), but easily tolerated.
Moderate	Discomfort to a degree as to cause interference with normal daily life activities and /or requiring medication.
Severe	Incapacity with inability to work or do usual daily life activities and requiring medical attention/intervention.

#### **15.3.1.2 Causal Relations of Adverse Event/Experience**

When determining the causal/effect relationship to a test material, the relationship will be described as "None," "Possible," "Probable," or "Definite." The following definitions will be utilized:

None	No association to a test material. Related to other etiologies such as concomitant medications or conditions or subject's known clinical state.
Possible	Uncertain association. Other etiologies are also possible.
Probable	Clear-cut association with improvement upon withdrawal of a test material. Not reasonably explained by the subject's known clinical state.

Definite	An Adverse Event with a clear-cut temporal association with exposure to study materials and cannot reasonably be explained by the subject's known clinical state. Association with study material is confirmed by laboratory if possible.
----------	-------------------------------------------------------------------------------------------------------------------------------------------------------------------------------------------------------------------------------------------

#### **15.3.1.3 Serious Adverse Event/Experience – During this Study**

A Serious Adverse Event/Experience is any adverse experience occurring that results in any of the following outcomes:

- Death;
- A life-threatening adverse drug experience;
- Inpatient hospitalization or prolongation of existing hospitalization;
- A persistent or significant disability/incapacity;
- Congenital anomaly/birth defect;
- An important medical event that may require medical or surgical intervention to prevent one of the previously listed outcomes.

#### **15.3.1.4 Unexpected Adverse Event/Experience**

An Unexpected Adverse Event/Experience is any adverse drug event/experience not listed in the current labeling for a test material or the current investigator's brochure. Where test product labeling or investigator's brochure is not available, anticipated experiences will be based on the known pharmacological/toxicological properties of a test material or ingredients.

#### **15.3.2 Follow-up**

If an Adverse Event/Experience occurs, the subject under the direction of the Investigator (or designee) may be referred to the nearest acute care facility for treatment. All Adverse Events will be followed to resolution. Any Adverse Event will be documented on an Adverse Event Report Form.

#### **15.3.3 Notification**

The Sponsor and the reviewing IRB will be notified of all adverse event/experiences. Any Serious or Unexpected Adverse Drug Event/Experience that occurs during the study must be reported immediately by the Investigator to the Sponsor and the reviewing IRB, followed by written notification within 24 hours of the information being reported to the investigative study team.

The Principal Investigator, [name], and Medical Expert(s) are required to review all unanticipated problems involving risk to volunteers or others, serious adverse events, and all subject deaths associated with the protocol and provide an unbiased written report

of the event. At a minimum, the Principal Investigator and Medical Expert(s) must comment on the outcomes of the event or problem, and in the case of a serious adverse event or death, comment on the relationship to participation in the study.

#### **15.4 Anticipated Reactions**

The risks associated with this test are primarily related to application of a test material. Mild abrasion may occur due to cylinder sampling. Adhesive reactions are also possible. Mild skin irritation is anticipated and in some cases mild to heavy erythema, swelling, itching, cracking, peeling, or in rare cases, blistering and/or an allergic reaction might occur.

### **16.0 STATISTICAL METHODS**

#### **16.1 Data Sets Analyzed**

The Intent-to-Treat (ITT) Population will consist of all subjects who pass the pre-test period prior to baseline screening and are assigned a subject number for treatment. The ITT population (all randomized subjects) will be used for the safety analysis.

The modified Intent-to-Treat (mITT) Population will consist of all subjects who have at least one site (left or right for abdominal or inguinal) that passed the treatment day baseline (baseline values between  $3.0 \log_{10}$  -  $5.5 \log_{10}$  CFU/cm^2 on the skin on the abdomen, or  $5.0 \log_{10}$  -  $7.5 \log_{10}$  CFU/cm^2 on the skin on the inguen) and has CFU results for any other sample time for that site. The mITT data set will include all sites that passed the treatment day baseline bacterial counts and have CFU results for any other sample time. The mITT data set will be evaluated for efficacy.

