\* Note: For Screening Day baseline, the maximum upper limit does not apply. Only the minimum must be met.

Responder rates will be calculated separately for the abdomen and groin and separately for each test material and time point for each subject. The individual responses will then be grouped to generate an overall responder rate for each anatomical area for each test material. The efficacy goal for active test materials (test product and positive control) is to have the lower bound of the 95% confidence interval for the responder rate to be greater than or equal to 70%.

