## **12.0 SUBJECT WITHDRAWAL AND DISCONTINUATION**

The Investigator (or Subinvestigators) may discontinue individual subjects from the study at any time. Subjects may voluntarily withdraw from the study at any time without reason or consequence. The subject will be asked to report the reason for withdrawal. The Investigator will provide a written report on the appropriate source document or Case Report Form (CRF) including the date and reason for discontinuance. Subjects who qualify on Screening Baseline Day and begin the treatment phase may not be re-entered into the study, regardless of whether or not they completed the study.

Any enrolled subject will be discontinued for the following reasons:

1. A skin irritation rating of 3 for any individual skin condition at any evaluation following the application of study treatment. (A skin irritation rating of 2 for any individual skin condition at any evaluation following the application of study material may also be the cause for subject discontinuation at the discretion of the Investigator).
2. Experiencing a serious protocol deviation that compromises the data results, for example, using a topical antibiotic at a test site during the study.

Reference Sections 13.3, 13.9 and 17.3 for handling of withdrawn subject data.

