### **17.3 Procedures for Accounting for Missing Data**

Missing microbiological data at 30 seconds, 10 minutes, or 6 hours will be reported as missing; if the entire sample is missing the site will be treated as a nonresponder for that sample time. These subjects will be included in the mITT data set based on the criteria defined above. Details of any other missing data handling will be specified in the statistical analysis.

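### A treated site with no post-treatment count leaves the responder-rate denominator, while a site missing only its 10-minute sample counts as a nonresponder

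*Combined protocol and SAP*

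**What the plan says.** Section 16.1 (Data Sets Analyzed) defines the modified intent-to-treat set at two levels. A subject enters with at least one site that passed the treatment-day baseline and has a count at some other sample time. The site-level rule is the same and admits only "sites that passed the treatment day baseline bacterial counts and have CFU results for any other sample time". The section then assigns the sets: "The mITT data set will be evaluated for efficacy" and "The ITT population (all randomized subjects) will be used for the safety analysis". No intent-to-treat efficacy analysis is planned, and no sensitivity analysis covers sites outside the modified set.

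Section 17.3 gives the missing-data rule for 30 seconds, 10 minutes and 6 hours: "if the entire sample is missing the site will be treated as a nonresponder for that sample time". Its scope follows: "These subjects will be included in the mITT data set based on the criteria defined above".

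Section 7.1 sets the primary goal for each active material in each anatomical area, at 10 minutes: "lower bound of the 95% confidence interval for the responder rate to be greater than or equal to 70" per cent. Section 16.2 calls for exact intervals.

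Section 12.0 lists among the mandatory reasons for discontinuation "A skin irritation rating of 3 for any individual skin condition at any evaluation following the application of study treatment", and sends the reader to Sections 13.3, 13.9 and 17.3 for withdrawn subjects' data. Section 13.5 and the flow chart in Section 7.6 place a skin evaluation before every post-treatment sample, including the one at 30 seconds.

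**The concern.** The two sections treat the same kind of loss in opposite ways. A site that loses one or two post-treatment samples stays in the denominator and fails at the times it missed. A site that loses all three disappears from the analysis. The second site provides less evidence of effect than the first, yet only the first counts against the product.

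This is an exclusion based on what happens after treatment, and it acts on a single-proportion test against 70%. The positive control follows the same rule, but that does not cancel the effect, because each active material is judged against 70% on its own count. Measured against the plan's own nonresponder rule, the exclusion can leave the rate unchanged or raise it; it cannot lower it.

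**Working it through.** **Inputs.** Section 11.1: at least 288 subjects with both active materials, and at least 32 in each of the two vehicle pairings. Section 7.1: lower 95% bound of at least 70%. Section 16.2: exact interval. Two assumptions: the interval is two-sided Clopper-Pearson, since the method is not named, and the number of no-count sites is varied, since the documents give no expected figure.

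**The plan's own counts.** 288 + 32 + 32 = 352 subjects; 352 × 2 sides = 704 sites per body area; 288 + 32 = 320 sites per active material; 32 + 32 = 64 vehicle sites. These agree with Section 11.1. The text of Section 7.4 is not available, so no power figure can be reproduced.

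**Pass mark.** For x responders among n sites, the lower bound is the 2.5% quantile of a Beta(x, n − x + 1) distribution. At n = 320, 240 responders (75.0%) give 69.88% and fail; 241 (75.3%) give 70.21% and pass.

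**No-count sites on top of 320 analysed sites.** Section 11.1 enrols until the required evaluations are complete, so this is the closer match to the plan. Under 16.1 the result stays 241/320. With k no-count sites scored as nonresponders it becomes 241/(320 + k):

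| k | Rate | Lower bound |
|---|---|---|
| 0 | 75.3% | 70.2% |
| 1 | 75.1% | 69.97% |
| 3 | 74.6% | 69.5% |
| 6 | 73.9% | 68.8% |
| 16 | 71.7% | 66.6% |

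**No-count sites within 320 treated sites.** If 1, 3 or 5 of the 320 have no count, the smallest passing results under 16.1 are 240/319, 239/317 and 237/315 (lower bounds 70.1%, 70.3% and 70.1%). With the same sites scored as nonresponders, 240, 239 and 237 out of 320 give 69.9%, 69.6% and 68.9%. All three fail.

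**Away from the threshold.** The smallest number of added no-count sites that reverses a pass:

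| Observed | Sites needed |
|---|---|
| 243/320 (76%) | 4 |
| 250/320 (78%) | 14 |
| 256/320 (80%) | 22 |
| 272/320 (85%) | 44 |
| 288/320 (90%) | 66 |

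**Chance of a false pass.** Suppose the true rate, with missing counted as nonresponse, is exactly 70%. If a fraction d of sites has no count, the rate among analysed sites is 0.70/(1 − d). The probability of at least 241 responders among 320 analysed sites is 2.1% at d = 0, 3.9% at d = 1% (rate 70.7%) and 6.8% at d = 2% (rate 71.4%). These values of d are assumptions.

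**Against the unobserved truth.** Take d = 2% and 80% response among analysed sites. If a fraction m of the lost sites would have responded, the bias is 0.80 − (0.98 × 0.80 + 0.02 × m) = 0.02 × (0.80 − m). That is +1.6 points at m = 0, +0.6 at m = 0.5, zero at m = 0.8 and −0.2 at m = 0.9.

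**The case against.** The best defence is that such a site should be rare. All three samples must be lost. The 30-second and 10-minute samples are both due before the remaining sites are dressed and before the subject has to come back at 6 hours (Section 13.5). Failure to return at 6 hours therefore does not trigger the exclusion. A severe reaction first scored before the 10-minute sample does not either, provided the 30-second count exists: the site stays in the set, and a missing 10-minute sample counts as nonresponse. Section 12.0 also points withdrawn subjects' data to 17.3. All of this stands and keeps the gap narrow. It does not close the gap, because 17.3 refers back to the 16.1 criteria.

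A second objection is that the condition on post-treatment data serves other analyses. The log10-reduction ANOVA and the average-treatment-effect (ATE) regression have no outcome for a site without a count, and nonresponder status cannot supply one. This stands, and it limits the fix to the responder analyses.

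Two stronger readings are tempting. A reader might infer that the primary rate is biased upward as a matter of fact. The documents do not support that: they do not say that any such site will occur, and the sign against the true rate depends on how lost sites would have responded. A reader might also infer that a site rated 3 at the first skin evaluation necessarily leaves the efficacy set. Section 12.0 requires discontinuation but does not say whether the sample then due is still taken, so this is a possible route and an inference.

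**Conclusion.** The inconsistency between 16.1 and 17.3 is real but minor. If treated sites with a valid treatment-day baseline and no post-treatment count occur, the 10-minute responder rate is higher than the plan's own missing-data rule would give. One such site is enough to reverse a result exactly at the pass mark of 241/320. At 80% observed response it takes 22, and at 90% it takes 66.

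This rests on a two-sided Clopper-Pearson interval and 320 analysed sites per active material and body area. That few such sites are likely is a judgement from the sampling schedule. The same exclusion applies to all three materials, so its effect on differences between treatments has no fixed direction.

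**What to change.** For the responder-rate analyses only, define the set as all treated sites that passed the treatment-day baseline. This means removing the post-treatment-data condition from both the subject and the site definitions in 16.1 and aligning the back-reference in 17.3. Apply the 17.3 nonresponder rule at every missing time, and report the number of no-count sites by material and body area. Keep the current set for the log10-reduction ANOVA and the ATE regression.

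The amendment of 29 August 2017 states that testing was already complete, so the responder analysis on the wider set should be reported as a sensitivity analysis beside the planned one. No new data are needed. The cost is a second analysis set to define and a slightly lower responder rate if such sites occurred.

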#### **16.2 Efficacy (Primary) Analyses**

CFU values will be calculated as per Section 13.9. Individual plate CFU counts that are zero will be treated as 0.5 for further calculations. Changes from baseline will be calculated separately for each subject and for each of the three non-baseline sites by taking the baseline  $\log_{10}$  CFU/cm^2 values and then subtracting the  $\log_{10}$  CFU/cm^2 values for the samples taken after the baseline. Therefore, a subject who completes all treatments and passes all baseline requirements will have 4 (sites) \* 3 (post-application samples per site) = 12 changes from baseline reported. Responder status will be calculated for each reported  $\log_{10}$  CFU/cm^2 reduction. The sites will be considered responders based on the sample time and body area:

For the groin at 30 seconds or 10 minutes, a  $\log_{10}$  CFU/cm^2 reduction  $\geq 3.0$  is considered a responder.

For the abdomen at 30 seconds or 10 minutes, a  $\log_{10}$  CFU/cm^2 reduction  $\geq 2.0$  is considered a responder.

For either the groin or the abdomen at 6 hours, a  $\log_{10}$  CFU/cm^2 value less than baseline (i.e., a  $\log_{10}$  CFU/cm^2 reduction  $> 0$ ) is considered a responder.

Responder statuses will be grouped by body area, sample time, and test substance. Exact confidence intervals will be calculated for responder rates. The primary efficacy goal is to have the 95% confidence intervals for the responder rate at 10 minutes to be  $\geq 70\%$ . The secondary efficacy goals are to have the 30-second and 6-hour 95% confidence intervals for the responder rates to be  $\geq 70\%$ .

Differences in responder rates between treatments and their confidence intervals will be calculated using asymptotic (approximate) methods. If differences in responder rates are not reliable based on approximate methods, which happens when rates are near either 100% or 0%,  $\log_{10}$  CFU/cm^2 confidence intervals for the differences will be used for comparison instead.

Two-sided confidence intervals for  $\log_{10}$  CFU/cm^2 changes from baseline will also be calculated. These calculations will use an ANOVA model with subject as a random variable and test substance as a fixed variable. Body area (abdomen or groin) will be a fixed variable. Sample times (30 seconds, 10 minutes, or 6 hours) will be calculated separately using identical models. Differences in  $\log_{10}$  CFU/cm^2 reductions will be calculated based on the same model.

Any deviation(s) from the statistical analysis plan will be described and justified in the final report.

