### **13.9 Data Handling**

The estimated  $\log_{10}$  number of viable microorganisms per  $\text{cm}^2$  recovered from each sample site will be designated the "R-value."

To convert the volumetric measure of the sample into the number of colony-forming units per square centimeter ( $\text{cm}^2$ ), the following formula will be employed:

$$R = \log_{10} \left[ \frac{F \left( \frac{\sum c_i}{n} \right) 10^{-D}}{A} \right]$$

Where:

$R$  = the average colony-forming unit count in  $\log_{10}$  scale per  $\text{cm}^2$  of sampling surface

$F$  = total number of mL of stripping fluid added to the sampling cylinder; in this study,  $F =$  [REDACTED]

$\frac{\sum c_i}{n}$  = average of the duplicate colony counts used for each sample collected

$D$  = dilution factor of the plate counts

$A$  = inside area of the cylinder in  $\text{cm}^2$ ; in this study,  $A =$  [REDACTED]

**NOTE:** The reason that a  $\log_{10}$  transformation will be performed on the collected data is to obtain a linear scale. A linear scale, more appropriately a  $\log_{10}$  linear scale, is a basic requirement of the statistical models used in this study.

If colonies on one of the plates is uncountable, the count from the remaining plate will be used.

Colony counts of 0 will be set to 0.5 for further calculation purposes. The average for duplicate plates each containing 0 CFU's would result in an average of 0.5 CFU's further used for calculating the R Value.

Data collected from subjects with low or high test-day baseline counts on an anatomical test site ( $< 3.0 /> 5.5 \log_{10}$  CFU/ $\text{cm}^2$  from the skin of the abdomen, or  $< 5.0 /> 7.5 \log_{10}$  CFU/ $\text{cm}^2$  on the skin on the groin) will not be used in the Efficacy Analyses (Section 16.2). This is a common occurrence in clinical-simulation studies. Hence, more subjects will be enrolled and tested to account for test-day baseline failures.

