Average Treatment Effect (ATE) will be estimated from a linear regression of post-treatment bacterial count ( $\log_{10}$  scale) on the additive effect of a treatment indicator and the baseline or pretreatment measurement ( $\log_{10}$  scale). ATE will be calculated for the 10-minute samples separately for each product and each body area. [REDACTED]

The ATEs will be compared as follows:

- a. ZuraPrep™ will be compared to the ChloraPrep®. To show effectiveness, ZuraPrep™ should be non-inferior to ChloraPrep® with a 0.5 margin. Specifically, the upper bound of the 95% confidence interval of the ATE of ChloraPrep® minus the ATE of ZuraPrep™ should be less than or equal to 0.5.
- b. ZuraPrep™ will be compared to ZuraPrep™ vehicle. To show effectiveness, ZuraPrep™ should be superior to ZuraPrep™ vehicle by a 1.2 margin. Specifically, the lower bound of the 95% confidence interval of the ATE of ZuraPrep™ minus the ATE of ZuraPrep™ vehicle should be greater than or equal to 1.2.

The same ATE calculations will be performed for the 30-second time point, but the results are for informational purposes only.

PROTOCOL AMENDMENT FORM

DATE: 08/29/2017

PROTOCOL NUMBER: 150316-103

APPROVALS:

[REDACTED]

  
STUDY DIRECTOR / PRINCIPAL INVESTIGATOR

08/29/17

DATE

[REDACTED]

REVIEWED BY:

[REDACTED]

[REDACTED]

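### Zero colony counts entered as 0.5 in the 10-minute ATE regression could hide a true ZuraPrep deficit, mainly on the abdomen, if many ChloraPrep samples show no colonies

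*Combined protocol and SAP*

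**What the plan says.** Section 13.9 sets the rule: "Colony counts of 0 will be set to 0.5 for further calculation purposes". It adds: "The average for duplicate plates each containing 0 CFU's would result in an average of 0.5 CFU's further used for calculating the R Value". Section 16.2 repeats the rule for the efficacy analyses: "Individual plate CFU counts that are zero will be treated as 0.5 for further calculations".

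The 08/29/2017 amendment, issued after testing was complete, adds to Sections 7.1 and 16.2: "Average Treatment Effect (ATE) will be estimated from a linear regression of post-treatment bacterial count" on the log10 scale, with a treatment indicator and the baseline count as terms. It specifies that "ATE will be calculated for the 10-minute samples separately for each product and each body area".

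Two effectiveness criteria follow. ZuraPrep "should be non-inferior to ChloraPrep® with a 0.5 margin", judged on "the upper bound of the 95% confidence interval of the ATE of ChloraPrep® minus the ATE of ZuraPrep™". It also "should be superior to ZuraPrep™ vehicle by a 1.2 margin". The two subtractions make sense together only if a larger ATE means a larger reduction, and that reading is used here.

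No readable text treats zero counts as censored, asks for their frequency, or plans a sensitivity analysis. One redacted span directly follows the sentence on calculating the ATE by product and body area.

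**The concern.** A sample with no colonies on either plate tells us only that the count lies below the detection limit. The rule gives every such sample the same value, however far below the limit it lies. That does little harm to the responder endpoint, for which the rule was already in place, because a sample at the floor will normally have met the required reduction.

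It matters more once a difference in mean log10 counts becomes a criterion. If ChloraPrep reduces counts further than ZuraPrep, more ChloraPrep samples reach the floor and more of its effect goes unrecorded. The observed deficit moves toward zero, and the variance also falls, which narrows the interval. When ZuraPrep is truly worse by the margin, both changes make it easier for the upper bound to fall at or below 0.5. At stake is whether a non-inferiority finding would reflect the products or the limit of the assay.

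**Working it through.** **1. The plan's own figures.** Sections 7.0 and 11.1: 288 + 32 + 32 = 352 subjects; 352 × 2 = 704 sites per body area; 288 + 32 = 320 sites per active; 32 + 32 = 64 for vehicle. All agree. No power or SD is readable in Section 7.4, so only the counts can be checked.

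**2. Where the floor lies.** One colony over two plates is a mean of (1 + 0)/2 = 0.5, so a zero-zero sample is entered at the detection limit itself. A sample with one colony and one empty plate becomes (1 + 0.5)/2 = 0.75. By the Section 13.9 formula, undiluted, the floor is log10(0.5·F/A). F and A are blacked out. Assuming F/A between 0.5 and 3 mL/cm², it lies between log10(0.25) = −0.60 and log10(1.5) = 0.18.

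- Abdomen, baseline 3.0: largest recordable reduction 3.0 − 0.18 = 2.82 to 3.0 + 0.60 = 3.60, which is 0.82 to 1.60 above the 2.0 responder threshold.
- Groin, baseline 5.0: 4.82 to 5.60, which is 1.82 to 2.60 above the 3.0 threshold.

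Zero-zero samples are therefore responders in both areas over this range.

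**3. Direction.** Let the latent log10 count above the floor be normal with SD s and mean m for ChloraPrep, m + D for ZuraPrep. The recorded value is max(Y, 0), with mean m·Φ(m/s) + s·φ(m/s). The slope of this mean in m is Φ(m/s), which is below 1, so the recorded difference is smaller than D. If D = 0 there is no bias.

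**4. Size with a clean floor.** The second moment is (m² + s²)·Φ(m/s) + m·s·φ(m/s). With 320 sites per product, P(pass) = Φ((0.5 − d)/SE − 1.96), where d is the recorded difference.

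Example: 25% ChloraPrep zeros, s = 1.0, D = 0.5. Then m = 0.6745; the means are 0.824 and 1.234, so d = 0.410; the variances are 0.627 and 0.807; SE = √(1.434/320) = 0.067. P(pass) = Φ(0.090/0.067 − 1.96) = 27%.

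| ChloraPrep zeros | Recorded d, SD 1.0 | False pass, SD 1.0 | False pass, SD 0.8 to 1.5 |
|---|---|---|---|
| 0% | 0.50 | 2.5% | 2.5% |
| 10% | 0.47 | 6.4% | 5–7% |
| 25% | 0.41 | 27% | 17–33% |
| 50% | 0.30 | 97% | 82–99% |
| 70% | 0.20 | 100% | 100% |

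With a true deficit of 0.75, a false pass is about 0% at 25% zeros, 2 to 10% at 50% and 94 to 97% at 70%.

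**5. Size with counting noise.** Simulated Poisson duplicate plates, each zero set to 0.5, true deficit 0.5, SD 0.8 to 1.0, independent or paired sites. The share is that of ChloraPrep samples with no colonies:

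- almost none: about 2–3% false passes
- 5–8%: 4–7% (2–4% if the fit ignores pairing)
- 14–18%: 14–30%
- about 30%: 76–90%

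These exceed the clean-floor values at the same share, because a single empty plate is raised too. For comparison, the step 4 formula at 30% zeros and SD 1.0 gives d = 1.104 − 0.715 = 0.389, SE = √((0.564 + 0.759)/320) = 0.064 and a false pass of 41%.

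**6. Does a censored fit help?** On clean-floor data (SD 1.0, deficit 0.5, 1,000 runs), a left-censored regression estimates 0.50 and passes falsely in 2.4%, 3.0% and 2.6% of runs at 25%, 50% and 70% zeros. The planned fit estimates 0.41, 0.30 and 0.20 and passes in 27%, 98% and 100%. This is the model the censored fit assumes, so it is a favourable test. With counting noise some shrinkage should remain, since samples with one empty plate are raised but not censored.

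**The case against.** The strongest reply is that nothing in the documents shows that the floor is reached often. The zero share and the SD are not given, and F and A are blacked out. This stands: the large percentages describe what would happen at assumed shares, and below about 10% zeros the test stays close to nominal.

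Second, most sites are left/right pairs. A fit that ignores a within-subject correlation of 0.3 starts at 0.4% rather than 2.5%, which offsets the inflation when zeros are rare. It does not rescue higher shares: the same setting gives 25% at 25% zeros and 99% at 50%.

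Third, the groin is largely spared. Assuming SD 1.0, mean groin baseline 6.0 to 6.5 and a 3-log responder rate of 75 to 90%, zeros there are about 0 to 6%. They reach about 15% only with a mean baseline of 5.5 and the highest assumed floor. This stands and confines the point mainly to the abdomen.

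Fourth, the amendment says that the FDA recommended this regression and its margins, and a difference in recovered counts is a legitimate target in its own right. A difference below detection is a different quantity that rests on an uncheckable distribution. This is a good reason not to make a censored fit a condition of success, but no reason to leave the sensitivity unexamined.

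Finally, the responder rate remains the stated primary measure, and ZuraPrep must also beat vehicle by 1.2 log10, where the floor works against success. Both limit the harm.

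**Conclusion.** The point holds conditionally. If ZuraPrep is truly worse and a material share of ChloraPrep's 10-minute samples have no colonies, the substitution raises the chance of falsely declaring non-inferiority. The direction follows from the rule and the model. The size does not follow from the documents. At a true deficit of 0.5, SD 0.8 to 1.0 and 320 sites per product, the risk is near nominal to about 7% below 10% zeros, about 15 to 30% at 14 to 18%, and about 75 to 90% near 30%, whether or not pairing is modelled. These figures assume Poisson plates; a clean floor gives lower values at the same share. Deficits well beyond the margin, such as 0.75, would often pass only with zeros in the majority.

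A reader might infer more than this, and the documents do not support it:

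- That the non-inferiority test is known to be invalid: the share of zeros is unknown.
- That the floor always favours ZuraPrep: there is no bias if the products are equal, and a true ZuraPrep advantage would shrink as well.
- That both body areas are equally exposed: the groin's baseline range sits 2 log10 higher.
- That the plan certainly lacks a provision for censoring: the redacted span cannot be read and cannot be counted as an omission.

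**What to change.** Keep the linear regression as the stated ATE analysis and leave the responder analysis unchanged. Add to the ATE text in Sections 7.1 and 16.2:

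- **Zero share.** Report the percentage of samples with zero colonies on both plates, by product, body area and sampling time.
- **Sensitivity analysis.** Fit the same model (treatment plus baseline, by body area, with the left/right pairing accounted for) as a left-censored regression, with zero-zero samples censored at the detection limit. Specify it in writing before the fit is run.
- **Reporting rule.** If the 0.5 non-inferiority conclusion does not hold in that fit, the report says so and qualifies the conclusion.

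Do not make the censored fit a second pass/fail criterion. The cost is a paragraph of amendment text, one table and one more model on data already collected. The drawback is a normality assumption below the detection limit that the data cannot verify. If zeros are rare, the two fits should agree and the non-inferiority claim is stronger for it.
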